### Pulmonary Toxicity

- For ≥ grade 3 pulmonary infiltrate, interrupt midostaurin for the remainder of the cycle.
   Resume midostaurin at the same dose when infiltrate resolves to ≤ grade 1.
- Missed doses of midostaurin will not be made up.

### Other Grade 3 / 4 Non-Hematologic Toxicity

- For other grade 3 / 4 non-hematologic toxicities that are considered to be at least possibly related to midostaurin, interrupt midostaurin. Resume midostaurin at the same dose when toxicity resolves to ≤ grade 2. If midostaurin is held for more than 28 days, then discontinue midostaurin continuation therapy.
- Missed doses of midostaurin will not be made up.

## Other Grade 1 / 2 Non-Hematologic Toxicity

- Persistent grade 1 or 2 toxicity during continuation therapy that patients may deem unacceptable may prompt a drug holiday for as many as 28 days. No drug holidays longer than 28 consecutive days will be allowed.
- Missed doses of midostaurin will not be made up.

### Daunorubicin Cardiac Toxicity Dose Modifications

Daunorubicin should not be given in case of case any of the following symptoms have a possible relationship according to the investigator's judgement:

- Symptoms of heart failure
- Reduction of the left ventricular ejection fraction below 50%
- Superventricular arrhythmias and/or morphologic changes in the ST period or T wave or low voltage in QRS or prolongation of QT interval

## 7.2.2 High-Dose Cytarabin Consolidation Therapy Dose Modifications

Contributions of concomitant medications to neurotoxicity should be assessed and other medications discontinued if possible.

For neurotoxicity  $\geq$  grade 2 due to high-dose cytarabine during consolidation therapy, discontinue high-dose cytarabine for the remainder of the cycle. High-dose cytarabine may be considered at the next consolidation therapy cycle with a dose modification from 3 g/m^2 to 2 g/m^2 if the toxicity has resolved to  $\leq$  grade 1.

For a second occurrence of neurotoxicity  $\geq$  grade 2, high-dose cytarabine should be permanently discontinued.

### 7.2.3 Dose Modifications for Obese Patients

There is no clearly documented adverse impact of treatment of obese patients when dosing is performed according to actual body weight. Therefore, all dosing is to be determined solely by the patient's BSA as calculated from actual weight. This will eliminate the risk of calculation error and the

possible introduction of variability in dose administration. Failure to use actual body weight in the calculation of drug dosages will be considered a major protocol deviation. Physicians who are uncomfortable with administering chemotherapy dose based on actual body weight should not enrol obese patients.

## 7.3 Concomitant Treatment/Medication

There is no restriction for any medically necessary concomitant treatments or medications. Physicians should be aware that midostaurin is a competitive inhibitor of CYP3A4/5. Studies also show CYP3A4 is the major human p450 enzyme catalyzing biotransformation of midostaurin. Thus, co-administration of drugs which are potent inducers (e.g. phenytoin) or, especially, potent inhibitors (e.g. itraconazole) of this isoenzyme could decrease or increase midostaurin concentrations, and, potentially, decrease the effectiveness or increase toxicity, respectively. A list of agents that may have potential drug interactions is given in appendix 2.

### 7.4 Study Evaluations

	Screening examination within 7 days before study entry	Day 1of 2 nd induction and Day 1 of each consolidation	Day 1-28 of 2 nd induction and each consolidation	Remission control†	Start maintenance	During maintenance	Within 14 days after end of maintenance	Follow-up 3, 6+9 months after end of maintenance	Relapse
Screening Examination	х								
Check In- and Exclusion Criteria	х								
Registration	х								
Toxicity Assessment (AE)			х		х				
Toxicity Assessment (SAE)			х		х	Monthly	Х	х	
Physical Examination incl. blood pressure, pulse and weight	х	x			x	monthly	х	х	
CBC (incl. differential and plts)	х	x	2x/week	х	x	monthly	х	х	х
Chemistry and Coagulation: Na, K, Ca, Crea, Mg, Urea, ALAT, ASAT, AP, Bili, Total Protein, Albumin, Uric Acid, Glucose, INR, PTT, Fib	х	x	2x/week		x	monthly	x	х	х
fT4, TSH	х								
Urinalysis	х								
Bone marrow cytology	х			х		Q 3 months *		х	х
Bone marrow cytogenetics	х			х		Q 3 months *		х	Х
Bone marrow molecular genetics	х			х		Q 3 months *		х	х
EKG (QTc Interval)	х	Х	**		**	**			
Chest X-Ray (pa and lateral)	х								
Echocardiography (LVEF)	х								
Beta-HCG pregnancy test	х								
Concomitant Medication			Х			х			

† latest day 35 after beginning of each course of chemotherapy

\* and in case of suspected or overt relapse for confirmation

\*\* days 1,3,14 of midostaurin during induction 2 and each cycle of consolidation (days 8,10,21 of induction 2 and consolidation) and monthly during maintenance

Molecular and cytogenetic analyses will be done in the central SAL reference laboratory. With each bone marrow aspiration, material for central MRD diagnostics should be obtained and sent to the following address:

Universitätsklinikum Carl Gustav Carus, Medizinische Klinik und Poliklinik I, Hämatologisches Labor [name], [contact], [contact].

For information on results, please contact [name]. [name], [contact].

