## 4.3 Study Treatment

This is a one-arm open-label study, i.e. all included patients will receive the same treatment:

Patients with non-refractory chemo-responsive disease after one cycle of standard 7+3 induction treatment will enter the study before commencing second induction treatment. Standard induction treatment is defined as a seven-day continuous infusion of 100-200 mg/m^2/d plus three doses of daunorubicine, or idarubicine, or mitoxantrone. Chemo-responsive non-refractory disease is defined by reduction of blast count and/or cellularity on the early bone marrow assessment on day 14-16 of the first induction treatment and peripheral blast clearance, i.e. the absence of myeloid blasts in peripheral blood on day 14-16 of the first induction treatment. The first cycle of induction treatment after initial diagnosis is not part of this trial.

After inclusion in the study, patients will receive one cycle of standard DA (days 1-7) in combination with midostaurin treatment (days 8-21). After confirmation of responsive disease and complete remission, patients will continue with three cycles of high-dose cytarabine (HiDAC, days 1, 3, 5) in combination with midostaurin (days 8-21), which shall be administered depending on adequate blood counts and sufficient organ function. After a minimum of 14 days after the last midostaurin application in the last cycle of MidoHiDAC, i.e. earliest on day 36 after the beginning of the last cycle of MidoHiDAC, patients shall commence maintenance treatment. Maintenance treatment consists of 12 cycles with 28 days per cycle, i.e. continuous midostaurin application for a total of 336 days. After a maximum of 12 cycles midostaurin maintenance, patients will be followed up for additional 9 months. If patients stop study treatment or maintenance prematurely, i.e. before having completed 12 cycles of midostaurin maintenance, patients will be followed up until 25 months after study entry.

### For details, see section 7

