#### **MidoDA**

Cytarabine	100 mg/m  IV over 24 hrs	days 1-7
Daunorubicine	60 mg/m  IV over 1 hr	days 3-5
Midostaurin	50 mg/m  (2 capsules) p.o. twice daily	days 8-21

Midostaurin 50 mg (two 25 mg capsules) is given twice a day by mouth on days 8-21. Patients should take their doses at approximately the same time each day, and approximately 12 hours should elapse between the morning and evening doses. Each daily dose should be given with food and a glass of water (approx. 240 ml). Patients should be instructed to swallow capsules whole and not chew capsules. If vomiting occurs, no re-dosing is allowed before the next scheduled dose.

For **response assessment**, a bone marrow aspirate (or bone marrow biopsy) must be performed one week after recovery of ANC  $\geq$  1000/µL and platelets  $\geq$  100,000/µL to document a complete remission. Remission assessment must be performed latest 35 days after the beginning of second induction, even if ANC or platelets are below the described threshold.

If response assessment shows < 5% myeloid blasts, the patient has achieved a CR/CRi and will continue consolidation treatment according to this protocol.

If response assessment reveals  $\geq$  5% myeloid blasts, the patient will be classified as primary refractory disease and will discontinue study treatment. Patients who discontinue study treatment will be followed up until 25 months after study entry.

At each bone marrow aspiration, material should be obtained and sent to the central SAL laboratory in Dresden for MRD diagnostics (see section 7.4).

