### **MidoHiDAC**

Cytarabine	3000 mg/m  IV over 3 hrs twice daily	days 1,3,5
Midostaurin	50 mg (2 capsules) p.o. twice daily	days 8-21

High-dose cytarabine (HiDAC) 3000 mg/m^2 will be given by intravenous infusion over 3 hours every 12 hours on days 1, 3, and 5. Serial neurologic evaluation will be performed before and following the infusion of high-dose cytarabine.

It is recommended to administer dexamethasone 0.1% or other corticosteroid ophthalmic solution 2 drops to each eye four times per day to begin 6-12 hours prior to the initiation of the cytarabine infusion and to continue for at least 24 hours after the last cytarbine dose.

Midostaurin 50 mg (two 25 mg capsules) is given twice a day by mouth on days 8-21. Midostaurin is not given from day 22 of the current cycle and day 7 of the next consolidation cycle. Patients should take their doses at approximately the same time each day, and approximately 12 hours should elapse between the morning and evening doses. Each daily dose should be given with food and a glass of water (approx. 240 ml). Patients should be instructed to swallow capsules whole and not chew capsules. If vomiting occurs, no re-dosing is allowed before the next scheduled dose.

For **remission assessment**, a bone marrow aspirate (or bone marrow biopsy) must be performed one week after recovery of ANC  $\geq$  1000/µL and platelets  $\geq$  100,000/µL to document a complete remission. Remission assessment must be performed latest 35 days after the beginning of each consolidation cycle, even if ANC or platelets are below the described threshold.

If remission assessment shows < 5% myeloid blasts, the patient has a sustained CR/CRi and will continue treatment according to this protocol.

If remission assessment reveals  $\geq$  5% myeloid blasts, the patient has a relapse from CR/CRi and will discontinue study treatment. Patients who discontinue study treatment will be followed up until 25 months after study entry.

At each bone marrow aspiration, material should be obtained and sent to the central SAL laboratory in Dresden for MRD diagnostics (see section 7.4).

Three cycles of MidoHiDAC shall be administered depending on adequate blood counts and sufficient organ function.

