### Further safety examinations

A regular toxicity assessment will be obtained as outlined in the study evaluations (7.4) and in chapter 10. Furthermore, the primary endpoint of this trial, event-free survival is a combined efficacy and safety endpoint and will therefore also be used for the assessment of safety.

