## **10** Handling of Adverse Events (AEs)

### 10.1 Definition/Documentation of (Serious) Adverse Events

### 10.1.1 Definition and Documentation of AEs

An adverse event (AE) is any untoward medical occurrence in a patient or clinical investigation subject administered a pharmaceutical product and which does not necessarily have a causal

relationship with this treatment. An AE can therefore be any unfavourable and unintended sign (including an abnormal laboratory finding), symptom, or disease temporally associated with the use of a medicinal (investigational) product, whether or not related to the medicinal (investigational) product. In this context it must be especially stressed that any change in laboratory findings or vital functions, which leads to the discontinuation of the subject's treatment with the investigational medicinal product or to the termination of the clinical trial, must always be documented as an AE.

The investigator will monitor the development of adverse clinical events or pathological laboratory findings until recovery or stabilisation of the subject's condition.

Irrespective of any causal relationship, all adverse events spontaneously reported by the subject or observed by the investigator will be continuously documented in the medical record and on the designated case report form (AE form) during the clinical trial/at each follow-up visit. AEs will be documented from the first administration of study drug up to 30 days after the last administration. Classification of AEs will be done according to the CTC-AE classification, Version 3.0. Suspected relationship of between the AE and the study drug midostaurin or daunorubicin or cytarabine will be documented by the investigator.

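### The visit schedule marks no AE assessment after the start of maintenance, which conflicts with section 10.1.1 and risks uneven collection of non-serious AEs

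*Protocol*

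**What the plan says.** The schedule appears twice, before section 1 and again in section 7.4. Its two toxicity rows, "Toxicity Assessment (AE" and "Toxicity Assessment (SAE", read the same way in both copies:

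| Column | AE row | SAE row |
|---|---|---|
| Days 1-28 of second induction and each consolidation | marked | marked |
| Start of maintenance | marked | marked |
| During maintenance | blank | monthly |
| Within 14 days after end of maintenance | blank | marked |
| Follow-up at 3, 6 and 9 months | blank | marked |

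Section 10.1.1 sets a wider window for AEs: "AEs will be documented from the first administration of study drug up to 30 days after the last administration". It also says that AEs which a subject reports or an investigator sees "will be continuously documented in the medical record and on the designated case report form (AE form) during the clinical trial/at each follow-up visit".

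Section 9.2, under further safety examinations, relies on both places: "A regular toxicity assessment will be obtained as outlined in the study evaluations (7.4) and in chapter 10".

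Section 13.2.2 defines toxicity, a secondary target variable, as the incidence of AEs.

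**The concern.** The table and the text give sites different instructions for the longest phase of midostaurin treatment, and section 9.2 does not resolve the difference. Section 10.1.1 covers events that a subject volunteers or the investigator happens to observe; the schedule is what prompts staff to ask. A site working mainly from the schedule would be prompted only for SAEs once maintenance is under way, while a site working from section 10.1.1 would record all AEs.

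The events most exposed to this are symptoms. Section 8.4.2 lists nausea, vomiting and fatigue as the most frequent midostaurin-related events, and routine blood tests do not reveal them. Section 7.2.1.4 also makes maintenance decisions depend on graded toxicity, including persistent grade 1 or 2 toxicity, so the protocol needs these events to be noticed in this phase. With 18 patients, up to 25 or more centres and no concurrent control arm, uneven recording between sites would tend to lower the reported AE incidence and could not be reliably repaired afterwards.

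**Working it through.** **Inputs**

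- Second induction (section 7.1, MidoDA): "Midostaurin 50 mg (two 25 mg capsules) is given twice a day by mouth on days 8-21". That is 14 days.
- Consolidation (section 7.1, MidoHiDAC): "Three cycles of MidoHiDAC shall be administered depending on adequate blood counts and sufficient organ function". Midostaurin is again given on days 8-21, so 3 × 14 = 42 days.
- Maintenance (section 4.3): "Maintenance treatment consists of 12 cycles with 28 days per cycle, i.e. continuous midostaurin application for a total of 336 days".
- AE marks: as tabulated above.

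**Step 1. Reproduce the protocol's figure.** 12 × 28 = 336 days, as section 4.3 states.

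**Step 2. Planned exposure.** 14 + 42 + 336 = 392 midostaurin days. Maintenance is 336/392 = 85.7%.

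**Step 3. Exposure without an AE mark.** The mark at the start of maintenance covers its first day, so the blank begins on day 2. Covered: 56 + 1 = 57 days (57/392 = 14.5%). Not covered: 336 − 1 = 335 days (335/392 = 85.5%).

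**Step 4. Sensitivity to the number of consolidation cycles.** Section 7.1 allows maintenance after two cycles. Planned exposure is then 14 + 28 + 336 = 378 days, and the uncovered share is 335/378 = 88.6%.

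**Step 5. Sensitivity to early stopping.** Induction and consolidation together give 56 days, which equals two maintenance cycles. Maintenance therefore exceeds half of a patient's exposure once more than 2 of its 12 cycles are taken.

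**Step 6. The same gap in calendar time.** Assume 28-day chemotherapy cycles, full maintenance, and a maintenance start between day 36 and day 64 of the last consolidation cycle (the bounds in section 7.1). Counting from day 1 of second induction, maintenance starts on day 84 + 36 = 120 or day 84 + 64 = 148, and ends on day 455 or 483. The AE window from the first midostaurin dose (day 8) to 30 days after the last dose is 485 − 8 + 1 = 478 or 513 − 8 + 1 = 506 days. The stretch after maintenance day 1, including the 30 days, is 335 + 30 = 365 days. The share is 365/478 = 76% or 365/506 = 72%. If the window instead opens with the first chemotherapy dose (day 1), it is 365/485 = 75% or 365/513 = 71%.

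**Step 7. Which blank cells fall inside the 30-day window.** The during-maintenance column and the visit within 14 days of its end do. The 3-, 6- and 9-month visits do not, although section 10.1.1 also mentions each follow-up visit. The cells that clearly conflict with the 30-day rule are therefore two in each table.

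**The case against.** The strongest reply is that the schedule is not the only instruction. Section 10.1.1 requires continuous AE documentation and section 9.2 names chapter 10 alongside section 7.4. A blank cell does not forbid recording, so a site would miss these events only by overlooking chapter 10. This stands. A reader might infer that non-serious AEs go uncollected in maintenance, or that about 86% of AEs would be lost; the protocol supports neither. The percentage describes planned midostaurin days, and no under-count can be derived from it.

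It is also true that maintenance is well observed. Physical examination, blood count, chemistry, coagulation and ECG are monthly, and section 10.1.1 requires any laboratory or vital-function change that leads to discontinuation to be documented as an AE. This narrows the gap to a missing prompt, chiefly for symptoms, but does not close it.

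A third reply is that the blank might come from how the table was converted to text. Agreement between the two copies is weak evidence against this, since the same layout could lose a merged cell twice. However, the AE row has its own marks in the two earlier columns, and the SAE row alone has three further entries. A lost merged cell for the monthly entry would not explain the blank end-of-maintenance cell as well. A look at the original table would settle it.

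Finally, the AE restriction could be deliberate for the intensive phase. The window in section 10.1.1 rules that out.

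**Conclusion.** The concern holds as an internal contradiction with a data-quality risk. The AE row of both schedules stops at the start of maintenance, section 10.1.1 runs to 30 days after the last administration, and section 9.2 invokes both. For a patient who completes all planned treatment with three consolidation cycles, 335 of 392 midostaurin days (85.5%) have no scheduled AE assessment. Patients who stop early have a lower share.

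The likely consequence is uneven under-collection of non-serious, mainly symptomatic AEs for the secondary endpoint of AE incidence. The primary endpoint and its decision rule are unaffected. The conclusion assumes that the tables as read match the original layout. It should be corrected, because the repair is small and the missing information could not be recovered reliably later.

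**What to change.** Reconcile the tables with section 10.1.1. In the AE row of both copies:

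- enter monthly under the during-maintenance column;
- add a mark under the visit within 14 days after the end of maintenance;
- add a footnote that AEs are collected to day 30 after the last study drug dose for every patient, including those who stop early.

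The footnote is needed for two reasons. The end-of-maintenance visit may fall well before day 30, and its column does not clearly apply to patients who stop before maintenance.

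The change is two cells in each of two tables plus the footnote. The monthly and end-of-maintenance visits already exist, so the cost is slightly more CRF entry. No dose or treatment rule changes.

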## 8 Investigational medicinal product: Midostaurin (PKC 412)

## 8.1 Description of the Investigational medicinal product

The study drug provided is midostaurin 25 mg. The study drug will be supplied by Novartis as soft gelatine capsules, packaged in child-resistant blisters. See Investigator's Brochure for further characteristics, mechanism of action, preclinical activity, side-effects, pharmacokinetics and Phase I studies and results of clinical trials.

### 8.2 Packaging and Labelling

Novartis is responsible for packaging, labelling, and shipping of study medication via the Drug Distribution Centre. Each blister contains eight (8) capsules and each medication kit contains eight (8) blisters for a total of sixty-four (64) capsules per kit. Each patient shipment will consist of 4 medication kits. Each kit has a 2-part label which looks like this:

labelling: medication kit	Sponsor: TU Dresden, 01062 Dresden, [contact] CPKC412ADE01T / TUD-MIDOKI-052 EudraCT-Nr. 2011-002567-17 PatNr. :
	PKC412 25 mg 8 x 8 Kapseln zum Einnehmen Nach Vorschrift Ihres Arztes einnehmen zwischen 2 und 8 °C lagern Bei einer Lagerung bei Raumtemperatur (nicht über 25°C) innerhalb von 3 Monaten anzuwenden verwendbar bis: MM/YYYY ChB.: XXXX
	Zur klinischen Prüfung bestimmt Arzneimittel für Kinder unzugänglich aufbewahren
	Zur Verlugung gestellt von. Novartis Pharma GmbH, D-90327 Numberg

labelling: blister	Sponsor: [name]. [name], Universitätsklinikum an der TU Dresden, 01307 Dresden CPKC412ADE01T / TUD-MIDOKI-052 PatNr. :			
	PKC412 25 mg 8 Kapseln zum Einnehmen ChB.: XXXX			
	Zur klinischen Prüfung bestimmt Zur Verfügung gestellt von: Novartis Pharma GmbH, D-90327 Nürnberg			

## 8.3 Provision, Storage and Dispensing

There will be a central drug distribution by Novartis. Sites are responsible for contacting the Drug Distribution Center to order study drug for individual patients included in this clinical trial. The amount of drug to be requested per shipment is 4 medication kits.

### Ordering:

There are no starter supplies. Midostaurin supplies are patient specific. Sites will complete the Drug Request Form available in the ISF, checking the "initial supply" or "resupply" box. The form will be faxed to Novartis, Germany:

### Storage and Dispensing:

Blister packs should be stored under refrigeration at 2-8°C and protected from light. After dispensing to the patient, midostaurin may be stored at home at room temperature (below 25°C) for as long as three months. Please note that each box of 8 blisters measures 194 mm x 122 mm x 65 mm. Upon opening a blister pack, patients may notice a pungent odor. The odor is due to ethyl thioglycolate that forms when ethanol in the capsules interacts with the thermostabilizer in the foil. The capsules are not affected, and the odor will dissipate.

The investigator will be responsible for ensuring the correct storage and sufficient stocks of the investigational medicinal product at the centre. Where allowed/required, the investigator may/should entrust the investigational medicinal product, in whole or in part, to an appropriate pharmacist (to be designated in advance) or another appropriate individual who is under the supervision of the investigator.

The investigator or a pharmacist, or another appropriate individual who is designated by the investigator, should maintain records of the delivery of the investigational medicinal product, the stocks at the study centre, the use by the individual trial subjects, and the return of unused investigational medicinal products to the sponsor or their disposal. The investigator should ensure that the investigational medicinal product is only used according to this protocol.

- The investigator bears the responsibility for the proper storage in an appropriate place to which unauthorised persons have no access.
- The investigator may only dispense the investigational medicinal product to subjects who have been enrolled in the study. The dispensing of the investigational medicinal product to subjects outside of this clinical trial is not permitted.
- The investigator, or an individual who is designated by the investigator, should explain the correct use of the investigational medicinal product to each trial subject and check at regular intervals that each subject is following the instructions correctly.

